7.3.5 Laboratory safety assessment

7.3.5.1 Methods of assessment

Blood samples will be collected for haematology, clinical chemistry, coagulation parameters, and safety monitoring. Urine samples will be collected for urinalysis. Unscheduled laboratory results, from tests pre-specified in this protocol, that are both abnormal and clinically significant will be recorded on an additional eCRF page(s) and the data will be included in the assessment of out of range parameters. The investigator will decide if the unscheduled laboratory results are “clinically significant”.

All blood and urine samples will be collected according to standard procedures at the timepoints scheduled in [Table 1](#) by the investigator or medically qualified personnel. Details on sampling and handling procedures for samples processed centrally will be specified in the study laboratory manual. Samples should be taken before dosing as applicable.

The parameters to be assessed are detailed in [Table 4](#).

For blood volume see Section [8.1](#)

Table 4 Laboratory safety parameters

Haematology ^a	Clinical chemistry ^a	Coagulation ^a	Safety monitoring	Urinalysis ^a
Haemoglobin	ALT	apTT	Troponin I	Protein
Haematocrit	AST	D-dimer	Multiplex renal panel	Blood
WBC with differential	GGT	Fibrinogen	Total HASA bridging assay	Ketones
Platelets	Alkaline phosphatase	International normalised ratio (PT)	HASA IgG	Microscopic analysis
	Serum albumin		Protein C activity	pH
	Creatinine		IgE ^c	Clarity
	Blood urea nitrogen		Tryptase ^c	Colour
	Total protein			Specific gravity
	Total bilirubin			Glucose
	Creatine kinase			
	Calcium ^b			
	Lactate dehydrogenase			
	Lactate			
	Sodium			
	Potassium			
	Chloride			
	Carbon dioxide			
	Glucose			

^a To be performed at local laboratory.

^b Calcium (total).

^c Tryptase and IgE are not routine safety parameters and will only be measured in the event of an infusion or hypersensitivity reaction, although IgE is being done routinely at screening.

Abbreviations: ALT = alanine aminotransferase; apTT = activated partial thromboplastin time; AST = aspartate aminotransferase; GGT = gamma glutamyl transferase; HASA = human anti-sheep antibody; Ig = immunoglobulin; PT = prothrombin time; WBC = white blood cell.

A blood sample for serum pregnancy testing will be taken from all females of child-bearing potential at screening. Patients may be entered into the study on the basis of a negative urine pregnancy test (sensitivity of at least 50 mIU/mL of β HCG), pending results of the serum pregnancy test. If the serum pregnancy test is positive, the patient must be discontinued from study treatment, unless post-partum.

Haematology, clinical chemistry, coagulation and urinalysis parameters will be analysed locally (d-dimer should be analysed using a quantitative assay) with the exception of those specified below.

Each laboratory (local and central) will be required to provide up-to-date reference ranges.

Collection of troponin I, protein C activity, IgE and tryptase

Blood samples for measurement of troponin I, protein C activity, IgE and tryptase will be collected according to standard procedures at timepoints specified in [Table 1](#) (or only in case of infusion or hypersensitivity reactions for tryptase, see [Appendix D](#)) by the investigator or medically qualified personnel. Details on sampling and handling procedures for samples processed centrally will be specified in the study laboratory manual.

Blood samples may be taken from a peripheral or central venous source or from an arterial source. The time that each blood sample is taken will be recorded in the eCRF. If a sample is missed, the next sample should be taken as scheduled.

Analysis of troponin I, IgE and protein C activity will be done centrally by Covance Central Laboratory Services, Inc.

Tryptase (if obtained for infusion or hypersensitivity reactions) samples will be analysed by Specialty Laboratories. All laboratory samples will be labelled, stored and shipped according to standard laboratory procedures.

Collection of Human Anti-Sheep Antibody (HASA) IgG and total HASA bridging assay

Blood samples for measurement of HASA IgG and total HASA by bridging assay will be collected according to standard procedures at timepoints specified in [Table 1](#) by the investigator or medically qualified personnel, according to methods specified by Covance or AstraZeneca. In addition, samples may be used for the improvement or development of further analytical assays related to AZD9773 or sepsis. Details on sampling and handling procedures will be specified in the study laboratory manual. Blood samples may be taken from a peripheral or central venous source or from an arterial source. The time that each blood is taken will be recorded in the eCRF. If a sample is missed, the next sample should be taken as scheduled.

Exploratory safety markers

Blood samples for plasma renal panel exploratory analysis will be collected according to standard procedures at timepoints specified in [Table 1](#) by the investigator or medically qualified personnel, according to methods specified by Covance or AstraZeneca. Details on

██████████
sampling and handling procedures will be specified in the study laboratory manual. Blood samples may be taken from a peripheral or central venous source or from an arterial source. The time that each blood is taken will be recorded in the eCRF. If a sample is missed, the next sample should be taken as scheduled.

A multiplex panel of established and exploratory markers of renal damage will be assessed. The plasma renal panel will be analysed by a third party vendor. Samples will be labelled, stored and shipped according to AstraZeneca Standard Operating Procedures.

7.3.6 Physical examinations

Physical examinations will be performed at Baseline and Day 29 (or the discharge visit if prior to Day 29) (Table 1) and reported in the physical examination page of the eCRF. The examination should be based on the following body systems: general appearance, skin, head and neck, lymph node, thyroid, musculoskeletal/extremities, cardiovascular, lungs, abdomen, and neurological. A minimum of a lung auscultation and dermal examination must be performed after each dose. Pulmonary auscultation must be performed by a medically qualified staff member who will listen to the patient's lungs to assess whether there is a change from baseline. A dermal examination will also be performed to assess for infusion reactions such as oedema, urticaria and rash. Additional findings of note will be recorded at this time. In the event of an infusion reaction (as evidenced by a change in BP, skin or lung examination), an additional full physical examination should be performed and changes (skin, lung, physical examination and BP) should be recorded in the eCRF.

Height will be recorded at screening. Weight will be recorded at the timepoints specified in Table 1. Screening weight will be measured as close as possible to the first dose but within 24 hours before the first dose.

7.3.7 Electrocardiogram

A digital 12-lead ECG will be recorded, in triplicate within 1 to 2 minutes, at the timepoints specified in Table 1 using equipment provided by the central ECG laboratory eResearch Technology, Inc (eRT). Patients must relax in a recumbent position for at least 10 minutes prior to the ECG reading being recorded. eRT will provide centralised processing of ECGs and data storage. Each ECG will define HR, PR interval, RR interval, QRS duration, QT interval, QTc (QTcF and Bazett [QTcB] corrections), T wave morphology (normal versus abnormal) and overall interpretation. eRT will contact the study centre if alert criteria are found on any ECG. Specific procedures for use of the ECG recorder and transfer process, as well as detailed alert criteria, will be provided in separate study documentation.

Abnormal values should not be recorded as AEs unless they result in discontinuation from the study or they fulfil the criteria for an SAE.

Abnormal QTcF values in relation to concomitant medications will be evaluated.

7.3.8 Vital signs, pulse, blood pressure and oximetry

Vital signs and blood oxygen-haemoglobin saturation will be collected at the timepoints specified in [Table 1](#).

Vital signs measured will include: BP (systolic and diastolic), pulse rate (PR), RR, and body temperature (oral, aural or core). The method of measuring body temperature must be recorded in the eCRF. BP, RR and PR will be measured after the patient has been in the supine position for 5 minutes.

The oxygen-haemoglobin saturation of the blood will be assessed using standard pulse oximetry or by arterial blood gas for those patients who have an arterial blood gas obtained.

Abnormal values should not be recorded as AEs unless they result in discontinuation from the study or they fulfil the criteria for an SAE.

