5.4 Withdrawal of patients

5.4.1 Criteria for discontinuation from the study treatment

Patients may be discontinued from study treatment at any time. Specific reasons for discontinuing a patient from study treatment are:

- Voluntary discontinuation by the patient who is at any time free to discontinue study treatment, without prejudice to further treatment (incapacitated patients may be withdrawn from study treatment by their legally authorised representative).
- AEs (eg, risk to patients as judged by the investigator and/or IDMC, CCC, PAREXEL or AstraZeneca).
- Severe non-compliance to protocol as judged by the investigator and/or CCC, PAREXEL, or AstraZeneca.
- See Section 5.3 for the procedures for handling incorrectly enrolled patients.

- Patient discharged from an adequately monitored setting.
- Positive pregnancy test (except for post-partum).
- Severe reaction to study drug infusion, or progressive, moderate reaction continuing to worsen, or the patient is refractory (eg, moderate reaction which does not respond to treatment) or at the discretion of the investigator ([Appendix D](#)) or study drug is not tolerated.
- Treatment is unblinded by the site investigator or designee.
- Need for immunosuppressant drugs and/or anti-TNF antibodies other than study drug. In the event of the need for these medications, the patient will be discontinued from study treatment but details of the medications (drug name, start date and time, dose, route of administration, stop date and time) will be collected for 28 days from the start of study drug (see Section [6.5.2](#) on concomitant medications).
- Dosing can be discontinued before all 10 doses are administered if the patient improves and maintains improvement for 24 hours (see Section [4.1](#)).

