5.4.4 Procedures for discontinuation of a patient from the study

A patient (or legally authorised representative will be asked in the case of incapacitated patients) that discontinues will always be asked about the reason(s) for discontinuation and the presence of any AE. If possible, they will be seen and assessed by an investigator(s). AEs will be followed up (refer to Sections 7.3.3 and 7.3.4). The reason for discontinuation from study drug or from the study must be recorded in the eCRF.

Patients who discontinue study treatment will be given appropriate treatment in accordance with institutional protocol and best practice. Every effort will be made to collect safety data from patients who discontinue.

Discontinuation of patients will be recorded in the Interactive Voice Response System (IVRS).

Procedures for discontinuation from study treatment

Patients who discontinue study drug should remain in the study and continue to have all scheduled assessments as shown in Table 1 (an assessment of all-cause mortality is required at Day 29 [+2] and Day 90, and a blood sample is required at Day 29 [-6/+14]) unless consent is withdrawn for participation in the study.

Procedures for discontinuation from study

In the case of withdrawal from the study, if possible, patients should be seen and assessed by an investigator. At the time of withdrawal, the procedures scheduled for the Day 29 Follow-up Visit should be performed, or Day 90 if the Day 29 Follow-up Visit has already occurred (see Table 1). AEs should be followed up as described in Sections 5.4.2, 7.3.3 and 7.3.4.

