Deterioration as compared to baseline in protocol-mandated laboratory values, vital signs and other safety variables should only be reported as AEs if they fulfil any of the SAE criteria or are the reason for discontinuation of treatment with the IP. However, the investigator may record such findings as an AE at his/her discretion in addition to completing an unscheduled laboratory/vital signs page with the information on the clinically significant test abnormality. If a deterioration in a laboratory value/vital sign is associated with clinical signs and symptoms, the sign/symptom will be reported as an AE and the associated laboratory result/vital sign will be considered as additional information. Any new or aggravated clinically relevant abnormal medical finding at a physical examination, dermal examination or lung auscultation as compared with the baseline assessment will be reported as an AE. Clinically relevant deterioration in

██████████
unscheduled assessments of laboratory/vital signs/ECG parameters should be reported on additional eCRF pages.

Wherever possible, the reporting investigator uses the clinical, rather than the laboratory term (eg, anaemia versus low haemoglobin value).

Overdose

Please refer to Section 1.2.

Pregnancy

Please refer to Section 1.3.

Deaths

All deaths occurring from provision of informed consent until Day 90 must be reported on the statement of death page. The cause of death may be reported as a SAE based on the criteria described in Section 7.3.2.

Follow-up of unresolved adverse events

After the initial AE/SAE report the investigator is required to follow up proactively each patient and provide further information to PAREXEL Clinical Studies Safety Centre on the patient's condition. During the study all AE/SAEs should be followed up to resolution or until the patient completes the study (ie, Day 90 or death) unless the event is considered by the investigator to be unlikely to resolve due to the patient's underlying disease (in these cases, the investigators must record their opinions in the patient's medical records), or the patient is lost to follow-up. Events still present at the time of death, and that were not the cause of death, should be classified as "ongoing". AstraZeneca and/or PAREXEL retain the right to ask for further information on any AE, which may be considered of interest.

Other significant adverse events

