13.3.9.2 Adverse events

AEs will be coded according to MedDRA.

TEAEs (events which were not present at baseline or worsened in severity following the start of treatment) will be presented. AEs occurring prior to the start of treatment will be listed only.

The following summaries will be provided:

- A summary of the number and percentage of patients reporting any TEAE, death, at least one severe TEAE, at least one serious TEAE, at least one TEAE possibly related to study drug, at least one TEAE leading to withdrawal from study drug, at least one infusion reaction (as defined in [Appendix C](#)), at least one hypersensitivity reaction by treatment group
- A summary of the number and percentage of patients reporting a TEAE by treatment group, system organ class (SOC) and preferred term
- A summary of the number and percentage of patients reporting a TEAE by treatment group and preferred term
- A summary of the number and percentage of patients reporting a TEAE by treatment group, intensity, SOC and preferred term. For each patient and each TEAE, the maximum reported intensity recorded will be attributed and used in the by-intensity summaries
- A summary of the number and percentage of patients reporting a TEAE by treatment group, by relationship to study drug, SOC and preferred term. The worst

relationship to study drug (most related to treatment) will be attributed and used in the by-relationship summaries

- A summary of the number and percentage of patients reporting an infusion reaction by treatment group, SOC and preferred term
- A summary of the number and percentage of patients reporting hypersensitivity reactions by treatment group, SOC and preferred term.

The following by-patient listing will be provided:

- A listing of all AEs (including non-treatment-emergent events), by treatment group and including centre, patient identifier, AE (SOC, preferred term, reported term), date of onset, date of resolution, duration, severity, seriousness, action taken, outcome and relationship to study treatment.

13.3.9.3 Deaths, serious adverse events, adverse events leading to withdrawal, and other significant adverse events

The following summaries will be provided:

- A summary of the number and percentage of patients reporting a serious TEAE by treatment group, SOC and preferred term.
- A summary of the number and percentage of patients reporting a TEAE leading to withdrawal from study treatment by treatment group, SOC and preferred term.

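### Sections 7.3.7 and 7.3.8 tell sites not to record as an AE a non-serious abnormal ECG or vital-sign value that stops study drug while the patient stays in the study; Section 7.3.3 requires one

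*Protocol*

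**What the plan says.** Three sections decide when an abnormal measurement becomes an AE.

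- **7.3.3 (recording of AEs).** The rule covers scheduled safety measurements, vital signs included, that have worsened since baseline. Such findings, it says, "should only be reported as AEs if they fulfil any of the SAE criteria or are the reason for discontinuation of treatment with the IP". Two further routes follow. One is discretion: "the investigator may record such findings as an AE at his/her discretion". The other applies where a worsened laboratory result or vital sign "is associated with clinical signs and symptoms, the sign/symptom will be reported as an AE".
- **7.3.7 (ECG) and 7.3.8 (vital signs and oximetry).** Both carry one identical sentence: "Abnormal values should not be recorded as AEs unless they result in discontinuation from the study or they fulfil the criteria for an SAE". Neither mentions investigator discretion, and neither refers back to 7.3.3.

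The protocol defines the two kinds of discontinuation separately. Section 5.4.1 lists reasons for stopping study treatment, AEs among them. Section 5.4.2 lists reasons for leaving the study: voluntary withdrawal, loss to follow-up and, before randomisation only, screening failure. Any other reason for leaving needs a prior discussion among named parties. Section 5.4.4 then states: "Patients who discontinue study drug should remain in the study and continue to have all scheduled assessments", unless consent is withdrawn.

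On the output side, 13.3.9.3 plans a summary of "patients reporting a TEAE leading to withdrawal from study treatment by treatment group, SOC and preferred term", and the overall AE summary in 13.3.9.2 has a line for the same kind of event.

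**The concern.** The trigger in 7.3.7 and 7.3.8 is leaving the study. The trigger in 7.3.3 is stopping the drug. Because stopping drug does not end participation, and an abnormal value is not among the listed reasons for leaving, the 7.3.7 and 7.3.8 trigger will rarely be met. A site that follows those two sections would not enter as an AE a non-serious abnormal value that caused dosing to stop. A site that follows 7.3.3 would.

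What is at stake is a tolerability output. An event not entered as an AE cannot appear in a table of treatment-emergent AEs leading to withdrawal from treatment. Safety and tolerability is a secondary objective, AEs are among the data the IDMC reviews, and about 100 centres could read the conflict differently.

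**Working it through.** No figure in the protocol depends on this rule, so there is nothing to recompute. The check is to take one type of event through each section.

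**Test event.** An abnormal ECG or vital-sign value that has deteriorated from baseline, is not serious, has no accompanying signs or symptoms, is not an infusion or hypersensitivity reaction, and leads to study drug being stopped while the patient stays in follow-up.

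| Section | Trigger | Is the trigger met? | Instruction |
|---|---|---|---|
| 7.3.3 | SAE criteria, or reason for stopping the investigational product | Yes, second limb | Report as an AE |
| 7.3.7 / 7.3.8 | SAE criteria, or leaving the study | No (5.4.4 keeps the patient in) | Do not record as an AE |

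A site cannot obey both.

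**Variations on the test event.**

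1. *It is serious.* All three sections call for an AE. No conflict.
2. *A deteriorated vital sign comes with signs or symptoms.* Under 7.3.3 the sign or symptom is itself the AE. The tolerability event is captured.
3. *It is part of a reaction to the infusion.* Appendix D lists completion of an infusion reaction AE form among the steps for any reaction, with no severity threshold, and 13.3.9.2 plans separate summaries of infusion and hypersensitivity reactions. An AE route exists.
4. *It does not stop dosing.* It is not a mandatory AE under 7.3.3 either, only a discretionary one. The one remaining difference is that 7.3.7 and 7.3.8 do not mention that discretion.

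The conflict on mandatory reporting is therefore confined to isolated, non-serious values that stop dosing and are not classed as infusion reactions.

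**Effect on the withdrawal table.** Let D be the true difference between an active arm and placebo in the percentage of patients whose only AE leading to withdrawal from treatment would be such an event. Let c be the share of these events that sites record as AEs, with 0 ≤ c ≤ 1. Assume c is the same in each arm, which is plausible because sites are blinded. The expected contribution to the table is then c × D instead of D. At c = 1 (every site follows 7.3.3) nothing is lost; at c = 0 (every site follows 7.3.7 and 7.3.8) the contribution disappears. Any distortion shrinks the absolute difference. The protocol gives neither c nor D, so no size can be attached.

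**The case against.** The strongest reply is that 7.3.3 is the section on recording AEs. It requires these events, allows discretionary recording as well, and nothing says that 7.3.7 and 7.3.8 override it. All study staff are expected to know the whole of Section 7.3, and 5.4.4 requires the reason for stopping drug to be entered in the eCRF. The wording may also be an editorial slip: 5.4.4 is headed as discontinuation from the study yet contains the procedure for stopping treatment. Prolonged QTc would still be visible by arm, because 13.3.9.6 tabulates QTc thresholds and ECG shifts whatever the AE status, and the IDMC sees individual and aggregated safety data.

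Much of this stands. It rules out three stronger readings that a reader might infer.

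- *That abnormalities which stop dosing will certainly go unrecorded.* The documents show two conflicting instructions, not which one sites will follow. The supported risk is inconsistent capture.
- *That an abnormal value is an AE only if it ends participation.* The sentence in 7.3.7 and 7.3.8 has a second limb for SAEs, so serious abnormalities are unaffected.
- *That severe infusion reactions, which Appendix D grades largely on vital-sign changes, would be lost.* Appendix D provides its own AE form for them.

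The reply does not remove the conflict. Even if it is a slip, a direct instruction not to record stands in the sections that site staff consult for ECGs and vital signs. The reason for discontinuation in the eCRF does not feed tables that count treatment-emergent AEs. The vital-sign summaries are only a partial substitute: Table 1 collects the values closest to 8 a.m., and 13.3.9.5 summarises scheduled assessments, so a change at another time of day may reach an unscheduled eCRF page without entering that summary.

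**Conclusion.** The inconsistency is real, and it is limited to isolated, non-serious ECG or vital-sign values that lead to stopping study drug in patients who remain in the study. The consequence is possible inconsistent or missing AE recording, with possible under-counting in the summaries in 13.3.9.2 and 13.3.9.3 of AEs leading to withdrawal from study treatment. The statement that an under-count would shrink the absolute difference between arms assumes equal recording practice across blinded arms.

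The size cannot be estimated. The protocol gives no rate of such events, and what it reports of earlier studies is comparable AE numbers on active drug and placebo. Any percentage-point figure would only restate assumed inputs. Nor do the documents say that the choice of regimen turns on this table; Section 4.2 frames that choice around ventilator-free days and dose-response. The point deserves correction because the wording is contradictory and cheap to repair, not because a large bias has been shown.

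**What to change.** In 7.3.7 and 7.3.8, change the first trigger from discontinuation from the study to discontinuation of study treatment, so that all three sections use the criterion in 7.3.3. Leave the SAE limb as it is. Add a cross-reference in both sections to 7.3.3, which brings in the discretionary and sign-or-symptom routes, and to the infusion reaction AE form in Appendix D, so that 7.3.8 is not read as barring vital-sign changes recorded there.

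The cost is one phrase changed in each of two sections, the cross-references and a note to sites. Slightly more AEs will be recorded. The change affects recording only; it does not touch dosing, the reasons for stopping treatment or the management of reactions.

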- j Within 3 hours prior to the first dose (preferably at the same time as the first pre-study drug infusion cytokine blood sample).
- k At screening but may be taken at any time during the study.
- l The baseline physical examination (including lung auscultation and dermal examination) should be done within 4 hours before dose administration.
- m A minimum of a lung auscultation and dermal examination must be performed after each dose. In the event of an infusion reaction (as evidenced by a causal change in BP, skin or lung examination), an additional full physical examination should be performed and changes (skin, lung, physical examination and BP) should be recorded in the eCRF.
- n Physical examination should be done at discharge if discharge is before Day 29.
- o One sample should be collected within 12 hours before dose administration (6 hours for lactate).
- p Record only if available and do not draw these laboratory blood samples if not available or required for other purposes.
- q Collect the sample at the routine collection time closest to 8 a.m.
- r In the event a patient experiences a hypersensitivity reaction, a blood sample for tryptase, IgE and quantitative eosinophil count should be obtained at 20 to 60 minutes post suspected infusion or hypersensitivity reaction and at Day 29.
- s There must be an interval of at least 6 hours between the lactate screening samples and the samples at Day 1. To preserve this minimum 6-hour window, the Day 1 samples may in fact need to be taken on Day 2.
- t ECG should be recorded as follows: baseline (pre-infusion Day 1; Day 1 end of infusion; Day 3 before first dose and end of infusion; Day 5 before first dose and end of infusion; Day 5 ECG 4-6 hrs after last dose; Day 10 at the same time as the PK sample; and Day 29 or at discharge. All ECGs will be obtained in triplicate within approximately 1 to 2 minutes, ensuring that the 3rd reading is prior to infusion start for pre-infusion measurements.
- u Collect only those values closest to 8 a.m.
- v PK blood samples should be taken as described in Section 7.7.1. Note: Some PK samples may need to be taken on the following day depending on the time of first dose administration.
- w Weight will be measured at screening as close as possible to the first dose but within 24 hours before the first dose. If the patient is discharged prior to Day 6, weight should be measured at discharge.

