(b) Recommended management in the event of a reaction to drug administration.

- Assess severity: mild, moderate, or severe (see Section IV for details).
- Stop infusion and consider treatment options (see Section V for details).
 - Include: observation, acetaminophen, diphenhydramine, steroids, epinephrine, fluids, albuterol, pressors, airway management and other measures in line with accepted medical practice as deemed necessary by the treating physician eg, iv histamine H2 receptor blockers.
- Monitoring (see Section VI).
- Consider restarting infusion after appropriate management and stabilisation or improvement in symptoms.
- Completion of infusion reaction adverse event (AE) form.

III Post infusion

(a) Monitoring

- A minimum of lung auscultation and dermal examination (eg, for oedema, urticaria, rash) should be done after the infusion is complete. In the event of an infusion of hypersensitivity reaction (as evidenced by a causal change in BP, skin or lung examination), an additional full physical examination should be performed and changes (skin, lung, physical examination and BP) should be recorded in the electronic Case Report Form.

- Laboratory parameter measurements
 - At timepoints according to the study plan (Table 1 of protocol).
 - Serum tryptase, IgE and quantitative eosinophil count, 20 to 60 minutes post suspected infusion or hypersensitivity reaction and repeated on blood draw at Day 29.
- (b) Classifying any infusion reactions
 - Timing
 - Early (onset during infusion or within 1 to 4 hours after infusion).
 - Intermediate (4 to 24 hours after end of infusion).
 - Delayed (onset from 24 hours to 4 weeks after end of infusion).
 - Severity (see Section IV).
 - Type
 - Timing: early, late or intermediate.
 - Hypersensitivity reaction versus infusion reaction.
 - (i) Any adverse reaction, which occurs within the dosing time, is potentially an infusion reaction.
 - (ii) A clinical picture of chills, rigors, fever, myalgia, wheeze, cough dyspnoea, altered vital signs or combination of signs and symptoms consistent with allergic phenomena/infusion reaction. Differentiation will be in immune system activation as evidenced by blood parameters eg, tryptase rise and response to slowing the rate of infusion: this will not affect a true hypersensitivity reaction.
- Investigate relationship of frequency, severity to:
 - History (eg, atopy, asthma, drug allergies).
 - Infusion rate.
 - Infusion concentration.
 - Infusion dose.
 - Infusion number.

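### Sections 7.3.7 and 7.3.8 tie AE recording of non-serious abnormal ECG and vital-sign values to leaving the study, whereas 7.3.3 ties it to stopping study drug, so some dose-stopping abnormalities could drop out of the count of TEAEs leading to withdrawal.

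*Protocol*

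**What the plan says.** **Specific rules.** Protocol 7.3.8 (vital signs and oximetry) ends with: "Abnormal values should not be recorded as AEs unless they result in discontinuation from the study or they fulfil the criteria for an SAE". Section 7.3.7 (ECG) carries the same sentence.

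**General rule.** Section 7.3.3, under AEs based on examinations and tests, covers laboratory values, vital signs and other safety variables. It makes a deterioration reportable as an AE only "if they fulfil any of the SAE criteria or are the reason for discontinuation of treatment with the IP". It then lets the investigator record such findings as AEs at discretion, and requires any accompanying sign or symptom to be reported.

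**Two kinds of discontinuation.** Section 5.4.1 lists reasons to stop study treatment, including AEs and "Severe reaction to study drug infusion, or progressive, moderate reaction continuing to worsen". Section 5.4.2 separately lists reasons to leave the study: voluntary withdrawal, loss to follow-up and, before randomisation only, screening failure. Section 5.4.4 keeps the two apart: "The reason for discontinuation from study drug or from the study must be recorded in the eCRF", and "Patients who discontinue study drug should remain in the study and continue to have all scheduled assessments".

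**Where the data go.** Section 13.3.9.2 counts by arm the patients with a TEAE leading to withdrawal from study drug and the patients with an infusion reaction. Section 13.3.9.3 breaks the withdrawal events down by system organ class and preferred term.

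**The concern.** The same finding meets two recording rules with different triggers. If leaving the study and stopping drug were interchangeable here, the difference would be cosmetic, but the protocol deliberately separates them and retains patients who stop drug. A value that ends dosing without being serious is then an AE under one section and should not be recorded as one under another, and a site cannot comply with both.

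At stake is a tolerability outcome. TEAEs leading to withdrawal from study drug are among the main by-arm safety summaries in a two-dose comparison with placebo. If sites differ in which section they follow, that count would depend partly on local reading of the protocol. No efficacy endpoint is touched.

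**Working it through.** The protocol gives no rate for such events and no figure to reproduce, so the check sets the rules side by side.

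**Step 1. One test case under each rule.** Take an ECG or vital-sign abnormality that is not serious, has no accompanying symptom, and leads the investigator to stop study drug while the patient stays in follow-up.

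| Section | Trigger other than seriousness | Is it an AE? |
|---|---|---|
| 7.3.3 | Reason for stopping treatment with the IP | Yes |
| 7.3.7 (ECG) | Discontinuation from the study | No |
| 7.3.8 (vital signs) | Discontinuation from the study | No |

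A serious event is recorded under all three, so the conflict is confined to non-serious events.

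**Step 2. How often can the trigger in 7.3.7 and 7.3.8 operate?** Section 5.4.2 does not list an abnormal value as a reason to leave the study, and any unlisted reason needs prior discussion between the coordinating centre, the medical monitor, the sponsor's physician and the investigator. Section 5.4.4 says patients who stop drug should stay. The trigger would rarely be met, and read literally 7.3.7 and 7.3.8 come close to a serious-events-only rule.

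**Step 3. Does another record supply the AE?** The reason for stopping drug must be entered in the eCRF (5.4.4), but that entry does not itself create a TEAE. The discretion in 7.3.3 permits recording without requiring it, and the other two sections advise against it. The sign-or-symptom clause in 7.3.3 does not reach an isolated abnormal value.

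**Step 4. What if the event is an infusion reaction?** Appendix D says "Any adverse reaction, which occurs within the dosing time, is potentially an infusion reaction", and its recommended management includes "Completion of infusion reaction adverse event (AE) form". A site that judges the event to be a reaction therefore has a separate AE route. The unprotected group is mainly abnormalities that stop dosing and are not so classed.

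**Step 5. Does limiting the rule to scheduled values remove the conflict?** For vital signs it helps: 7.3.8 refers to the Table 1 timepoints, and footnote u to that row asks only for values closest to 8 a.m. For ECG it does not. Footnote t schedules recordings around dosing: "Day 1 end of infusion; Day 3 before first dose and end of infusion; Day 5 before first dose and end of infusion". Counting all the times in that footnote: Day 1 has 2 (pre-infusion, end of infusion), Day 3 has 2, Day 5 has 3 (before first dose, end of infusion, 4 to 6 hours after last dose), Day 10 has 1, and Day 29 or discharge has 1. The total is 2 + 2 + 3 + 1 + 1 = 9, of which 3 fall at the end of an infusion. A scheduled ECG can therefore show an abnormality bearing on whether to continue dosing. This count shows only that the situation can arise; it says nothing about how many events would be lost.

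**The case against.** The strongest reply is that infusion reactions, the product-specific risk of a sheep-derived Fab, are well covered. A reader might infer that a reaction shown only by vital signs would be missed once it stops dosing. The documents do not support going that far:

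- Section 7.3.3 has its own heading on infusion reactions, which points to Appendix D, and Appendix D calls for an AE form.
- Section 7.3.6 requires a full examination and eCRF recording of blood pressure, skin and lung changes when a reaction occurs.
- Vital signs during a reaction come from the intensive monitoring in Appendix D, not from the daily value that 7.3.8 most naturally governs.
- A severe grade in Appendix D need not end dosing. Section 5.4.1 is permissive, and the appendix allows a restart to be considered after stabilisation.
- Section 7.3.3 prefers a diagnosis to a list of signs, and allows discretionary recording.

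These points stand, and they narrow the finding. Some residual risk remains: the AE form sits under recommended management, and 7.3.6 describes a reaction as evidenced by blood pressure, skin or lung changes, whereas Appendix D can grade a heart-rate change above 20 bpm alone as severe. That does not establish that reactions would be lost.

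It may also be said that 7.3.7 and 7.3.8 simply used the phrase loosely and meant study treatment. That is plausible, but the protocol distinguishes the two terms elsewhere, and sites work from the text.

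None of these replies reconciles 7.3.7 and 7.3.8 with 7.3.3 for a dose-stopping abnormality that is not classed as an infusion reaction.

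**Conclusion.** The contradiction is real. Followed literally, 7.3.7 and 7.3.8 could leave non-serious ECG or vital-sign abnormalities that stop dosing out of the by-arm count of TEAEs leading to withdrawal from study drug. The conclusion rests on three conditions: the event is not serious, it has no accompanying reportable sign or symptom, and the site applies 7.3.7 or 7.3.8 in preference to 7.3.3. It concerns mainly events not classed as infusion reactions. The number of patients affected is probably small and cannot be quantified from the protocol.

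The Appendix C reference in 13.3.9.2 adds no weight. Appendix C deals with sample shipment, other sections cite Appendix D correctly for infusion reactions, and the reference is an evident slip.

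This is a correction worth making because the rule is wrong as written and feeds a tabulated safety outcome. It is not evidence that the safety assessment as a whole is unreliable.

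**What to change.** 1. In 7.3.7 and 7.3.8, replace the study-discontinuation trigger with discontinuation of treatment with the IP, keep the seriousness criterion, and cross-refer to 7.3.3.
2. In both sections, add that suspected infusion or hypersensitivity reactions are recorded as AEs following Appendix D.
3. In 13.3.9.2, change the Appendix C reference for infusion reactions to Appendix D, as a clerical edit.

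The cost is wording in three sections, with no new data, visits or analyses.
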